## **6.3 Withdrawal or Discontinuation**

### **6.3.1 Slide Withdrawal**

It is unlikely that slides will be withdrawn from the study after they satisfy inclusion and exclusion criteria. However, if during the trial a slide somehow gets damaged or misplaced and cannot be used, or an inadvertent mix-up is discovered, this slide (or case) may be withdrawn and a protocol deviation noted. Such occurrence is expected to be very low. If necessary, another slide from the same case may need to be added or a new case may need to be enrolled in order to satisfy the overall number of cases examined for the trial. As long as the new slide does not change the recorded ground truth primary diagnosis and synoptic information of subtype, grade, margin and lymph node involvement, then the RP will not be asked to re-read cases already read. These events will be documented.

### **6.3.2 Case Withdrawal**

It is unlikely that cases will be withdrawn from the study after they satisfy inclusion and exclusion criteria. However, if during the trial a case can no longer be used, or an inadvertent mix-up is discovered, this case may be withdrawn and a protocol deviation noted. If necessary, a new case may need to be added to satisfy the overall number of cases examined for the trial. The substituted case shall be read by

all RPs for both modalities. These events will be documented. Such occurrence is expected to be very low.

### 6.3.3 Pathologist Withdrawal

If a reading pathologist is unable to complete the study reads according to study schedules, a replacement pathologist may be selected by Hamamatsu. In that situation there will be no re-reads of cases by the replacement pathologist (to be selected as similar as possible to the original pathologist), who will begin where the other pathologist left off, as long as the prior pathologist had completed reads for both modalities. The primary analysis will use all readings by the original/previous pathologist, with the readings by the replacement pathologist only being used for cases that the original/previous reading pathologist did not read with both modalities. Such occurrence is expected to be very low, but there is some possibility of staff turnover at any location.

## 7. DEVICE UNDER STUDY

### 7.1 System Description

The NanoZoomer S360MD Digital Slide Scanner System shall include:

[figure not shown]
1. The NanoZoomer unit to make whole slide digitized image scans of conventional histological glass slides of surgical tissue samples;
2. The software (C13220-01MD, version 1.0.0) to operate the scanner to create and store WSI images, as well as to view, manipulate, and annotate the digital WSI image on the monitor; and
3. The monitor for viewing the images.

The subsystems of the NanoZoomer system are connected over an information technology (IT) network. The IT hardware/software that supports the application software are not part of the system, but may be located in a central server room separate from the workstation with the viewing software and display. The communication of data between scanner and display may be linked by a customer-provided wired network or a direct connected cable between the systems. The display will be validated as part of the clinical study.

#### Key Specifications are:

Glass slide size	26mm x 76mm
Objective lens	20x (NA 0.75)
Scanning mode	20x mode / 40x mode
Scanning resolution / pixel	20x mode (0.46micron) / 40x mode (0.23micron)
Image acquisition	Color CMOS sensor
Light source	LED
Slide capacity	360 slides

NA = numerical aperture, CMOS = complementary metal-oxide semiconductor, LED = light emitting diode.

**Figure 4. Communication between Scanner and Display**

The Slide Scanner consists of the following blocks as shown above in **Figure 4**.

- **Slide Feeder:** The slide feeder is manually loaded with glass slides and then transfers glass slides from the slide cassette to the macro scanning position using the mechanical hand.
- **Macro Scan:** When the glass slide has moved to the macro image scanning position, the macro LED illuminates the slide and acquires the macro image of both specimen and barcode label. The scanning area is automatically determined based on the macro image.
- **Micro Scan:** After acquiring the macro image, the glass slide is moved to the micro image scanning position. Then the micro LED illuminates the slide, and focusing points are automatically detected, and the scanning of micro images starts. After the scanning has finished, the glass slide is moved back to the slide cassette.
- **Control Board:** The control board controls both the micro and macro cameras together with the focusing lenses.

[figure not shown]
## 7.2 General Principles of Operation

The Hamamatsu NanoZoomer S360MD Digital Slide Scanner ([Figure 5](#)) creates diagnostic quality digital images of glass slides containing FFPE tissue (11). Each image typically contains billions of image pixels, creating a digital image of the tissue on the original glass slide. The NanoZoomer captures digital images of entire slides for duplication, annotation, storage, retrieval, image sharing, and viewing to permit the pathologist to make a primary diagnosis without needing to view those glass slides through a light microscope.

The NanoZoomer can be loaded with as many as 360 glass slides with the mechanics of a slide feeder. The glass slide is transferred to the stage where the whole glass slide image is captured together with the barcode information present on each slide. Then the glass slide is moved to the scanning position. With the motorized stage, the 20x objective lens, the CMOS camera, and the LED, the NanoZoomer detects focusing points and scans the slide to acquire the digital slide image. During the scanning, the image is automatically stored on a hard disc. After scanning, the fully digitalized image can be observed with the viewing software.

The computer controls the scanner via camera link and universal serial bus (USB) interface. It also stores the images on a hard disk. After the scanning has finished, the images can be displayed on the computer's monitor.

The system software does not have any software application that does automated image analysis to aid in computer-aided detection of diagnosis.

**Figure 5. Example block diagram of typical components found in current WSI systems**

## 8. STUDY ASSESSMENTS AND PROCEDURES

### 8.1 Preparation of Facility

The sponsor shall install a complete Hamamatsu NanoZoomer System at each of the 4 sites. The system shall include the NanoZoomer Slide Scanner System, monitor, product software, and Operator's Manual. In addition to the components of the Hamamatsu NanoZoomer system, additional off-the-shelf components shall be used with the system, such as a designated computer, input device, and perhaps a sponsor's server or the site intranet for data storage.

The sponsor's product specialists shall ensure the devices are operational and that all sites have all proper records and any relevant certificates of manufacture. Likewise, the sponsor shall ensure any required maintenance is planned and conducted for the instruments prior to the start and during the course of study, as required. Sponsor will track the serial number of each NanoZoomer installed at each site. The Sponsor will retain at the site any shipping records for each device. Device accountability logs will be used to account for equipment at site. The Sponsor will maintain accountability of each device. All study records will be kept in a secure place at the site by the site coordinator.

The site IT department shall ensure there is proper and secure IT services for data storage of scanned images, recording of medical information, and retrieval of images for viewing, and for proper and secure use of electronic data capture (EDC) systems for data collection.

The WSI monitor viewing station cockpit and input device shall be standardized across all sites. Viewing images must be done at this defined monitor viewing station as the monitor is a required part of the NanoZoomer system as specified for the product and study.

The pathologist shall use the light microscope conditions normally used for reading of glass slides at the site.

## 8.2 Training on Study Procedures and WSI Operation

The sponsor, or its designated contract research organizations (CROs) or clinical professionals, shall conduct training according to pre-established and documented training modules, which may include:

- Selection of sites and pathologists to participate in study
- Shipment, installation, maintenance, and service of equipment by Hamamatsu personnel
- Screening and enrolling of cases, slides, and establishment of ground truth for non-inferiority study, recording of case notes to be made available to reading pathologist, training slides, and selection of self-familiarization slides
- Coding procedures for cases, slides, ground truth, and medical information selected for the enrolled case.
- Coding procedures for the reader pathologist chosen to participate in the study
- Storing, securing, and de-identifying Protected Health Information (PHI) for cases selected for study
- Use of WSI equipment for scanning and image storage, coordination with IT systems, and viewing workstation setup and operation
- Method to present case information available to pathologist
- Method to conduct of self-familiarization process
- CRO Installation, operation, and maintenance of EDC systems at site, validation and password protected access
- CRO Entering, storing, and securing data in electronic case report form (eCRF)
- CRO Randomization procedures for reading slides
- CRO Adjudication charter and process to adjudicate reader pathologists' diagnoses
- Documentation and reporting on device deficiencies and protocol deviations

- CRO Procedures for data management to manage the data integrity (data rejection, audit trail, verification, validation, and locking database)
- CRO GCP requirements training
- CRO GCP monitoring procedures

Training on Adjudication Process:

- Rules for Adjudication of “Major” and “Minor” discrepancies,
- CRO Operation of Adjudication Software

Each training event shall be recorded in a training log as to what training was done, who was trained, who did the training, where the training was performed, and the date of training. The training records shall be stored in a secure place by the study coordinator (SC).

Training shall include training of the:

- Entire site study staff (PI, sub-PIs, study coordinators, enrollment and validation enrollment pathologists, reader pathologists, WSI technicians, IT personnel) on study protocol, study processes, essentials of GCP, and human subjects training or applicable to those individuals.
- Study coordinators on proper storage of equipment, essential study GCP documents and records, eCRF and data records management.
- Technicians on operation of NanoZoomer scanner equipment, how to scan, review, check, annotate, and store scanned image, and training on what and how to fill out eCRF for scanning operation.
- Information Technology (IT) staff, if relevant, responsible for proper storage and retrieval of scanned images.
- EP on selection and validation of cases and slides for study, recording of ground truth, proper selection of slides from cases that demonstrate primary diagnosis, and collection of medical notes available to reader pathologist.
- VEP for review and confirmation of the cases, slides, supplemental information, and ground truth diagnosis selected by the EP.
- Reader pathologist (RP) on the protocol, study processes, instructions how to operate and view WSI slides for primary diagnosis, and how to fill out the eCRF for each case.
- Adjudication pathologists on procedures for adjudicating a) differences between EP and VEP enrollment case selection, and b) diagnosis of WSI and LM readings if identical to ground truth or discrepant and if any discrepancy is major or minor in respect to patient treatment.

Once trained, the reader pathologists shall be allowed to self-familiarize themselves in a mock primary diagnosis by WSI on a small set of training cases in order to become familiar with equipment operation. The pathologist will be allowed to conduct this trial diagnosis on 10 case slides chosen and selected per the same enrollment procedures for the cases for the study. Once the pathologist feels comfortable with the self-familiarization process, he or she may begin the study.

### 8.3 Selection of Case Slides

The site coordinator and/or EP shall search through the site’s database to locate and withdraw from the archive the assigned number of consecutive cases starting with archival cases at least 1 year old since accessioning and moving consecutively back in time. They will choose cases categorized from FDA in

**Table 2.** The EP will screen and enroll cases per the inclusion and exclusion criteria, to record the ground truth primary diagnosis, to record the FDA category information (i.e., organ, procedure, subtype, and category), record the basic patient case note(s) that the reader pathologist will be presented with, to select the slides indicative of primary diagnosis and to collect the supplemental diagnostic information and synoptic checklist information, where available in site pathology report, and relevant to classification, subtype, grade, margin, status, etc. The EP may consult with other pathologists within the site practice who may be subject matter experts in certain case categories, as long as those pathologists are not reader pathologists or VEPs. This supplemental information will be in accordance with truncated CAP cancer protocols (17) developed to highlight the key synoptic information to take into account later when reader pathologist makes study diagnosis.

GT diagnosis is the primary diagnosis based on the original sign-out (reported) primary diagnosis of cases that are enrolled in the study. The ground truth will not be reestablished, and should not include secondary diagnoses. Only a review of the final sign-out report (and not a review of the glass slides) will be used to record this information. The original sign-out primary diagnosis (reported clinically), as well as any supplemental diagnostic information, will be captured verbatim. If site uses synoptic checklists in their pathology report, that information, too, will be recorded.

From those cases, the EP will choose the H&E slide or set of H&E slides in the case that are consistent with the primary diagnosis. The following rules will be followed when selecting slides:

- For biopsy cases, the EP will select at least the H&E slides representative of the primary diagnosis. In most biopsy cases, this can be done with just 1 H&E slide, but the EP may choose more if needed to define the diagnosis. To minimize selection bias, the EP shall select the first H&E slide that encompasses that primary diagnosis.
- For resection cases, the EP shall select the set of slides that are necessary to indicate the primary diagnosis, inclusive of the key CAP checklist abridged metrics of cancer type, grade, margins and if metastasized to lymph nodes.
  - If there are multiple levels, the EP may select only the level of the same block slide that is germane to the primary diagnosis.
  - To minimize selection bias, the EP shall choose the first available H&E slide that describes that condition(s), rather than the best slide.
  - A minimum of 5 H&E slides will be selected. If the set of slides selected to define the primary diagnosis is < 5, then the EP shall continue to pick H&E slides until a minimum of 5 is achieved, and thereby the EP may pick further primary diagnosis slides, secondary diagnoses slides or slides irrelevant to any recorded diagnosis, whichever comes first.

In addition, for any case where there are extra slides with special and/or immunochemical stains, the EP shall enroll all those, as long as these extra stains are used for making/confirming the diagnosis and not for prognosis or to guide treatment (e.g. human epidermal growth factor receptor 2 [HER2] stain in breast cancer).

For enrolled slides, the EP shall remove all markings from the coverslip. If not possible, the slide shall be excluded, and another slide must be chosen.

*A priori* defined slide and case data rejection criteria have been developed per the defined inclusion and exclusion criteria in section 6. Some case data may be spurious or artifactual and may need to be disregarded, or slides may be damaged, aged, or lost, or there may be corrupted digital files, etc.

For every case enrolled, the EP shall make a determination if this case can be considered to be a “difficult and challenging” case. The EP will select “difficult and challenging” when one or more of the following apply:

- It’s professional opinion of EP that case is “difficult and challenging”
- Case used special stains or immunohistochemical stains to aid in diagnosis
- Case used molecular tests to aid in diagnosis
- Case used tumor boards to review case to aid in diagnosis
- Other reason, and brief narrative to elaborate.

The EP shall capture this information for every one of the 500 enrolled cases for that site.

#### **8.4 Validation of case and slide selection**

Upon completion of the screening and enrollment by the EP, then one validation enrollment pathologist (VEP) shall review and confirm the screening and enrollment selection of the EP. If the VEP disagrees with the case or slide selection of the EP, then both the EP and VEP shall meet for consensus decision. If agreement cannot be reached, then that case shall be disqualified.

All enrolled material and information shall be provided to the site coordinator for secure storage and to be kept blinded from reading pathologists.

#### **8.5 Storage of case slides**

The site coordinator shall:

- a. Collect and store the cases, slides and medical notes, clinical history of the case, and final pathology report in a secure location,
- b. Place proper de-identification labels (e.g., hide names, numbers, barcodes) on slides with a code known only to the site coordinator, and confirm those labels will not interfere with the scanning process nor affect the integrity of the tissue on the slide. The printer and label operations shall be validated before the study to prove the study labels do not interfere with the scanning process and are robust for the duration of the study, when the study labels can finally be removed and the material returned to the archive.
- c. Remove all patient identifiers and assign coded subject ID to protect patient privacy, and
- d. Ensure the traceability code-defining patient ID with study assigned code shall be kept only at the site, stored in a secure location, not shared outside the practice, and kept blinded to reading pathologists.

#### **8.6 Whole slide scanning operations**

The SC shall deliver the slides to be scanned to the scanning technician.

The scanning technician shall receive the batch of de-identified case slides to be scanned from the site coordinator. Then the technician shall:

- a. Scan the slide at 40x magnification according to the standard Hamamatsu default scanning conditions and save the image in its proprietary native file format.
- b. Conduct an initial quality check of the scanned slide to confirm that all material on the slide was properly scanned.
- c. Assess if the image looks to be of sufficient quality to advance to the pathologist.
- d. Transfer the WSI image to the assigned secure drive with proper file nomenclature consistent with the patient de-identified code.

If the technician deems that the scan quality is unsatisfactory, the technician may scan again, shall note that in the eCRF, review the slide quality of the re-scanned slide, and then store these images in the secure drive location. If re-scanning does not result in a suitable WSI, the technician shall note that in the eCRF, and then bring this to the attention of the EP and VEP to decide if that case or slide should be replaced. Data or re-scans will be recorded. Up to 5 scans will be allowed.

Once complete, all case and slide material shall be promptly returned to the coordinator for proper and secure storage. The WSI files shall be bundled into folders, each specific for each case.

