### 9.3 Populations for Analyses

**All Available Population (AAP):** AAP includes all cases for which at least one reader provides an evaluable outcome for either the WSI or Glass modality where an outcome is considered evaluable if the adjudication committee is able to classify the diagnosis as concordant, minor discordant, or major discordant with the Ground Truth diagnosis. If a reading pathologist is unable to complete study reads, a replacement pathologist may be selected by Hamamatsu, the re-reads by the replacement pathologist are supplementary, and the primary analysis will use all readings by the original/previous pathologist, with the readings by the replacement pathologist only being used for cases that the original/previous Reading Pathologist did not read by both modalities.

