### 10. DATA MANAGEMENT AND DATA QUALITY

#### 10.1 Data Management

The study shall have a data management plan to define how the data is handled, managed, stored, secured, and how the processes for that are validated, and how the access is controlled.

Case report forms (CRFs) and logs will be used to collect the data recorded in the course of the study, and shall be presented in an electronic data capture (EDC) system.

An eCRF for selection and enrollment of cases is to be completed for each case by the EP and confirmed by the VEP.

This information includes:

- Site ID, organ, procedure and subtype,
- Clinical history, age, gender, gross description notes
- Inclusion & exclusion criteria,
- Ground truth primary diagnosis, and diagnosis notes, and, where applicable, synoptic information of subtype, grade, margin and lymph node involvement
- Number of slides for the entire case, number of slides selected for the study, and organ of the slide, and stain for that slide
- Patient case notes.

An eCRF or log for WSI scanning operation for creation of WSI images to be filled out for each case by the technician scanning the glass slides which shall include:

- Clear instructions on what to do at what point along the way.
- Field entries for:
  - Date and Time
  - Name of technician
  - Site Name/Number
  - Case #
  - Slide # if there is more than one slide for the case
  - Condition of scanned image, if not acceptable, and why
    - If there is any gross out-of-focus, image aberration, color distortion, etc.
    - If all material was scanned.
    - If a rescan was required and why
    - If final scan acceptable
    - # of rescans

An eCRF for Primary Diagnosis recording to be filled out by the pathologist reader, which shall include:

- An eCRF for case and modality, with WSI-specific fields shown only for WSI cases

- Clear instructions on what to do at what point along the way
- Field entries for:
  - Date and Time
  - Site name/number
  - Case #
  - Slide # if there is more than one slide for the case
  - Tissue and organ and stain used
  - Clinical history, age, gender, gross description notes
  - ID of pathologist conducting reading
  - Start time and date of reader's review
  - Checkbox if reading by light microscope or WSI
  - Record of "Deferral" if to Glass, to specialist, or "Other" with free text field to describe.
  - Record of Primary Diagnosis:

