## 9. ANALYSIS POPULATION

### 9.1 All-Available Population (AAP)

The All-Available Population (AAP) includes all cases for which at least one reader provides an evaluable outcome for either WSI or Glass modalities.

Unless otherwise specified, All Available Population (AAP) will be used for all analysis.

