### 10.2 Disposition of Cases

The number of cases screened, eligible and enrolled will be tabulated by site and overall. The reasons for non-inclusion in analysis will be provided by site and overall.

The deferrals (e.g., deferral to specialist, deferral to glass, etc.) will be summarized by reader, site and overall for each modality. The reason for the deferral will also be provided in a listing.

The number and percentage of cases included in AAP will be summarized by site and overall.

The number and percentage of AAP cases read by each reader will be summarized for each site, if the full number of cases is not read.

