##### **11.1.2.2 Sensitivity Analysis**

Sensitivity analyses will be performed to evaluate the robustness of the primary analysis results. To perform the sensitivity analyses, the primary analysis model (1) will be analyzed with the following assumptions for deferrals and missing data observations:

- a) All deferred plus missing data observations assumed as major discordance with GT.
- b) All deferred plus missing data observations for WSI assumed as major discordance with GT and All deferred plus missing data observations for Glass assumed as no major discordance with GT

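### Does the worst-case sensitivity analysis miss scan failures when the case is replaced before any read?

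*Protocol*

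**What the plan says.** Protocol 8.6 allows up to five scans of a slide. If none is suitable, the technician records this and must "bring this to the attention of the EP and VEP to decide if that case or slide should be replaced". The section gives no rule for choosing between keeping and replacing. Protocol 6.3.2 adds that when a case can no longer be used, "this case may be withdrawn and a protocol deviation noted"; a substitute may be enrolled, and all readers then read it on both modalities.

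The analysis set is defined by reads. Protocol 9.3 states that the "AAP includes all cases for which at least one reader provides an evaluable outcome for either the WSI or Glass modality", and SAP 9.1 says the same: it "includes all cases for which at least one reader provides an evaluable outcome for either WSI or Glass modalities". SAP 9.1 applies this set to every analysis unless another is named, and SAP 11.1.2.2 names none.

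SAP 11.1.2.2 has two scorings. Analysis (a) counts every deferred or missing observation as major discordance. Analysis (b) is the least favourable to WSI: "All deferred plus missing data observations for WSI assumed as major discordance with GT", while "All deferred plus missing data observations for Glass assumed as no major discordance with GT".

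Several places cover reporting. SAP 10.2 states: "The number of cases screened, eligible and enrolled will be tabulated by site and overall"; it also gives the reasons for non-inclusion by site and overall. The scan form or log in Protocol 10.1 has a field for "Condition of scanned image, if not acceptable, and why", and records whether the final scan was acceptable. Protocol 9.4.4 tabulates technical issues, SAP 7 summarises deviations, and SAP 10.4 tabulates re-scan reasons.

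**The concern.** The primary analysis (SAP 11.1.2) drops deferred and missing reads, and SAP 11.1.2.1 also leaves out missing observations. Only the two sensitivity analyses can therefore hold a missing WSI result against the device, and (b) is meant to be the harshest. If a case leaves the study because the scanner could not produce a usable image, and a scannable case takes its place, (b) never sees the failure. Leaving such cases out of (b) can only favour WSI, and the decision is made at the site without a stated criterion.

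Had failures been common, (b) could have looked reassuring only because the worst cases had been exchanged before reading. What is at stake is whether (b) gives a fair picture. The primary non-inferiority conclusion is not touched.

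**Working it through.** **Inputs from the documents.** 2000 cases, 4 readers per case, 8000 planned reads per modality, margin 4%, two-sided 95% interval (Protocol 4.1, SAP 6 and 11.1.2). **Assumptions**, since the documents give no figure: the number k of cases replaced for scan failure, and major discordance rates near 5%.

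**1. Check of the variance formula.** Case-level variance: σ² = [π'WSI(1−π'WSI) + π'Glass(1−π'Glass)] × {1−λ+3(ξ−η)} / 4.
- At agreement 0.6, λ = 0.5, ξ−η = 0.15, Δ = 0: 2 × 0.24 × 0.95 / 4 = 0.114, as in SAP Table 2.
- At agreement 0.8, λ = 0.6, ξ−η = 0.10, Δ = 0: 2 × 0.16 × 0.70 / 4 = 0.056, also as in the table.
- The cell behind the 2000-case statement (0.6, 0.5, 0.15, Δ = −1.5%) computes to 1903.7 against the stated 1904.

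**2. Replaced cases added back into (b).** Each has four WSI reads scored major and four Glass reads scored not major. With a base difference of zero, the rise is k/(2000+k).

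| k | Rise (percentage points) |
|---|---|
| 1 | 0.050 |
| 5 | 0.249 |
| 10 | 0.498 |
| 20 | 0.990 |

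A random-intercept logistic model fitted to simulated data (both rates near 5%, site and reader variance set to zero) gave shifts of 0.246, 0.489 and 0.967 points for k = 5, 10 and 20. The simple formula is close enough.

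**3. Replaced cases added back into (a).** Both modalities are scored major, so the difference d₀ is only diluted: change = −d₀ × k/(2000+k). For d₀ = 1.5 points and k = 20 this is −1.5 × 20/2020 = −0.015 points.

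**4. Comparison with sampling error.** At 95% agreement, σ² runs from 2 × 0.0475 × 0.70 / 4 = 0.01663 to 2 × 0.0475 × 0.95 / 4 = 0.02256. The half-width 1.96 × √(σ²/2000) is 0.57 to 0.66 points. The shift in step 2 equals it at k = 11.4 to 13.3.

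**5. A failure that stays in the study.** Suppose all four readers defer the WSI read to Glass and read the Glass slides. The rise is k(1−g)/2000, where g is the Glass rate. At g = 5% that is 0.0475 points per case (0.0485 at 3%, 0.0465 at 7%). It is the same in (a) and (b), because both score the WSI reads as major and use the actual Glass result.

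**6. How many failures would matter against 4%.** This uses a case-level normal approximation (λ = 0.5, ξ−η = 0.15, reader correlation 0.5 among failed cases, Glass rate 5%) for failures that stay in. With equal true rates, the upper bound in (b) is about 1.2% at 10 cases, 1.7% at 20, 2.8% at 40, 3.8% at 60 and 4.9% at 80. With WSI truly 0.5 or 1.0 point worse, it crosses 4% between 40 and 60 cases. If the same cases are replaced, the bound does not move: 0.7% with equal rates, 1.2% and 1.7% in the other two settings.

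**The case for a change.** The strongest argument for a change is that a worst-case analysis should not depend on an unguided site decision. Two SAP sentences would settle it: show (b) with and without the replaced cases, and report their number. The data exist already, and showing both versions would let readers discount failures caused by slide defects. It is true that these cases are unscored and that their omission from (b) can only help WSI.

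The rest is weaker, for five reasons.

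- The sharpest contrast, between a replaced case and one kept and read on Glass alone, uses a route the documents do not describe. Protocol 8.7 has every reader read every case on both modalities. The documented way for a scan problem to be counted is a poor image that ends as a deferral to Glass.
- That counted route moves (a) as much as (b) (step 5), so amending (b) alone would not remove the inconsistency. Replacing only the slide also leaves the first scan failure unscored.
- Replacement has some bounds: the five-scan limit, the rejection criteria that Protocol 8.3 ties to section 6, and the need for a case to be unusable. A replacement made before any read cannot depend on how that case was read. That order is likely from the timeline in Protocol 4.3, though not stated.
- Under Protocol 8.4 enrolment is confirmed before scanning, so a replaced case is an enrolled case that is not analysed. SAP 10.2 already asks for that reason by site.
- The added-back result is fixed by construction. Anyone with the count can compute k/(2000+k). Scoring never-read and possibly defective slides as WSI major discordance, alongside their substitutes, is a debatable choice.

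**Conclusion.** The observation is correct, but it does not call for a change to the plan. A case replaced for lack of a suitable image before any read is outside the analysis set and unscored in both sensitivity analyses. A deferral to Glass is scored as WSI major discordance in both. The effect of adding replaced cases back is about 0.05 points per case in (b) and close to zero in (a). The primary analysis does not change.

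This is a gap that analysts can fill sensibly. When they tabulate reasons for non-inclusion under SAP 10.2, they can show cases and slides replaced for lack of a suitable image on their own line. A reader can then work out the effect on (b) from that count.

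The conclusion rests on replacements being few, as Protocol 6.3.1 and 6.3.2 expect of withdrawals, and on assumed discordance rates near 5%. If the tabulated count reached several dozen (2% to 4% of cases), (b) would need to be read together with that count.
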